c. I worry about bowel accidents.	1	2	3	4
d. I feel depressed.	1	2	3	4
e. I worry about others smelling stool on me.	1	2	3	4
f. I feel like I am not a healthy person.	1	2	3	4
g. I enjoy life less.	1	2	3	4
h. I have sex less often than I would like to.	1	2	3	4
i. I feel different from other people.	1	2	3	4
j. The possibility of bowel accidents is always on my mind.	1	2	3	4
k. I am afraid to have sex.	1	2	3	4
l. I avoid traveling by plane or train.	1	2	3	4
m. I avoid going out to eat.	1	2	3	4
n. Whenever I go someplace new, I specifically locate where the bathrooms are.	1	2	3	4

Q 4: During the past month, have you felt so sad, discouraged, hopeless, or had so many problems that you wondered if anything was worthwhile?

- 1 Extremely So - To the point that I have just about given up
- 2 Very Much So
- 3 Quite a Bit
- 4 Some - Enough to bother me
- 5 A Little Bit
- 6 Not At All

Fecal Incontinence Severity Index

Q 1: For each of the following, please indicate on average how often in the past month you experienced any amount of accidental bowel leakage:

	2 or More Times a Day		2 or More Times a Week		Once a Week	1 to 3 Times A Month	Never
	(1)	(2)	(3)	(4)			
a. Gas							
b. Mucus							
c. Liquid Stool							
d. Solid Stool							

Low Anterior Resection Syndrome Score – LARS Score. English version 1.0

Bowel function questionnaire

The aim of this questionnaire is to assess your bowel function.

Please tick only one box for each question. It may be difficult to select only one answer, as we know that for some patients symptoms vary from day to day. We would kindly ask you to choose one answer which best describes your daily life. If you have recently had an infection affecting your bowel function, please do not take this into account and focus on answering questions to reflect your usual daily bowel function.

Do you ever have occasions when you cannot control your flatus (wind)?

- No, never
- Yes, less than once per week
- Yes, at least once per week

Do you ever have any accidental leakage of liquid stool?

- No, never
- Yes, less than once per week
- Yes, at least once per week

How often do you open your bowels?

- More than 7 times per day (24 hours)
- 4-7 times per day (24 hours)
- 1-3 times per day (24 hours)
- Less than once per day (24 hours)

Do you ever have to open your bowels again within one hour of the last bowel opening?

- No, never

APPENDIX VI - HEALTH UTILITIES ASSESSMENT

Introduction

The assessment of overall health benefits is complicated by the need for a measure that can combine various benefits, such as overall survival, disease free survival, and quality of life into a single measure of benefit. Patients may value particular benefits differently. There is no obvious way to add together independently collected benefits for an individual or for a trial to yield a measure of overall benefit. Health utilities are a measure of how people value particular health outcomes. They provide a common denominator that can be combined with survival to form a measure of overall health benefits.

Such a measure of overall health benefit can then be used as part of a health economic analysis. Health economic analyses assess the benefits and costs of an intervention, for consideration whether the intervention may be worth its "costs" -- including financial, toxicity, and social costs.

The collection of information about health utilities is becoming more common in clinical protocols. In clinical trials, health utilities are most often collected using a patient self-reported questionnaire (similar to the collection of quality of life data).

Health utility and quality of life assessments provide different but complementary information.

- Health utility is a measure of preference for a given health state that acknowledges the risk and uncertainty of outcomes in choices patients face and in clinical decision-making.
- They can be used as a weighting factor to adjust survival by quality of life.
- Depending on whether a disease-specific or generic quality of life instrument is used, often only utility assessments may be able to compare patient groups with different diseases.
- Only utilities provide a single meaningful measure that can be incorporated in health policy and health economic analyses.

Health utilities data can be used in a variety of ways:

- to try and achieve the best possible outcome for patients and populations
- to evaluate the extent of change in health benefits of an individual, group, or population across time
- to evaluate new treatments, technologies, and patient management strategies
- to support approval of new drug applications or patient management strategies
- to try to provide the best value for health care dollars within and across diseases and health
- to compare costs and benefits of various financial and organizational aspects of health care services

In the future, approval of new therapies or patient management strategies will most likely be based on a combination of health benefit and cost data. This may be formally done using health utilities as part of a health economic analysis.

Instructions for Administration of a Health Utilities Questionnaire

The instructions below are intended as a guide for the administration of the Health Utilities Questionnaire

1. Preamble

Health utilities data are collected for research purposes, and will not be used for the patient's individual medical care. The assessment is in the form of a self report questionnaire. Therefore, it must be completed by the patient only, without translation, coaching or suggestions as to the "correct" answer by relatives or health care personnel.

The usual scheduled times to obtain the questionnaires are as follows:

- pre-randomization (baseline)
- during treatment
- during follow-up

The information provided by the patient in the completed questionnaire is confidential and should not be discussed with or shown to anyone who is NOT mentioned in the consent form signed by the patient.

If a particular question has not been answered, please document the reason(s) in the appropriate space on the questionnaire. If the whole questionnaire has not been completed, please document the reason(s) on the appropriate case report forms.

2. Pre-treatment Assessment

It should be explained to the patient that the purpose of the questionnaire is to assess the impact of treatment on different areas of the patient's life, eg: psychological distress, social disruption, symptoms, side-effects, *et cetera*.

The Clinical Research Associate (CRA) should collect the questionnaire as soon as it has been completed, check to see that each question has been answered and gently remind the patient to answer any inadvertently omitted questions. If a patient states that s/he prefers not to answer some questions and gives a reason(s), the reason(s) should be noted on the questionnaire. If a specific reason is not given, this also should be noted on the questionnaire.

3. Assessments During Treatment

The health utilities questionnaire should be given to the patient before being seen by the doctor, and prior to treatment, as required by the schedule in the protocol (not required during treatment for this trial).

4. Assessments During Follow-up

The health utilities questionnaire should be given to the patient before being seen by the doctor, on follow-up visits as required by the schedule.

A patient may, on occasion, be reluctant to complete the questionnaire because they feel unwell. In that case, you may express sympathy that things are below par, but state that this is exactly the information we require if we are to understand more about how overall health is affected. You may also remind them that it takes only a few minutes to complete.

It defeats the whole purpose of the assessment if it is delayed until the patient feels better!

5. What If...

The patient should complete the questionnaires at the clinic. The exception is that the design of some trials may require the patient to take the questionnaire home with them after leaving the clinic, and complete it on the specific day, because a return visit to the clinic is not scheduled.

There may be circumstances when the patient does not complete the questionnaire as required in the clinic. Four situations are described below. In these cases, it is beneficial if quality of life data can still be collected.

A. The patient leaves the clinic before the questionnaire could be administered, or someone forgets to give the questionnaire to the patient.

Contact the patient by phone informing him or her that the questionnaire was not completed. Ask the patient if s/he is willing to complete one:

If yes, mail a blank questionnaire to the patient, and make arrangements for return of the questionnaire in a timely fashion. Record the date it was mailed and the date received on the questionnaire.

If this is not feasible, then ask the patient if s/he is willing to complete a questionnaire over the phone. If the patient agrees, read out the questions and range of possibilities, and record the answers. Make a note on the questionnaire that the questionnaire was completed over the phone.

If no, note the reason why the questionnaire was not completed on the appropriate case report form.

B. The patient goes on an extended vacation for several months and won't attend the clinic for regular visit(s).

Ensure that the patient has a supply of questionnaires, with instructions about when to complete them, and how to return them. If it is known beforehand, give the patient blank questionnaires at the last clinic visit; if the extended absence is not known in advance, mail the blank questionnaires to the patient. Written instructions may help ensure that the patient stays on schedule as much as possible.

C. The patient does not want to complete the questionnaire in clinic.

Should the patient not wish to answer the questionnaire in the clinic but insists on taking it home, and failing to comply with the patient's wishes is likely to result in the questionnaire not being completed at all, then the patient may take the questionnaire home with instructions that it is to be completed the same day. When the questionnaire is returned, the date on which the questionnaire was completed should be noted and a comment made on the questionnaire as to why the patient took it away from the clinic before completion.

D. The patient is no longer attending clinic during the scheduled follow-up period.

Should the patient no longer be attending clinic, he/she should be contacted by phone to ask him/her to complete the questionnaire and mail it to the clinic. In order to facilitate this, ensure that after randomization all patients are provided with 2 blank questionnaires and 2 clinic-addressed stamped envelopes. When the questionnaire is returned, the date on which the questionnaire was received should be recorded on the questionnaire. The date on which the questionnaire was completed should be noted on the appropriate case report form, as well as where and why the patient completed the questionnaire outside of the clinic.

6. Inability to Complete Health Utilities Questionnaire (for reason other than illiteracy in English or French)

An eligible patient may be willing but physically unable to complete the questionnaires, because of blindness, paralysis, etc. If the patient is completing the EQ-5D assessment in the clinic, the questionnaire should be read to them and the answers recorded by a health care professional (e.g. preferably the clinical research associate assigned to the trial, but another clinic nurse, a doctor or social worker who is familiar with the instructions for administering the questionnaires would be acceptable). If the patient is completing the questionnaire at home, and a telephone interview by the clinical research associate is not possible, then a spouse or friend may read the questions to the patient and record the answers. However, this method should be a last resort, and the spouse or friend should be instructed to not coach or suggest answers to the patient. Whichever method is used, it should be recorded on the questionnaire.

If these special arrangements are not possible or feasible, then the patient would not be required to complete the questionnaires, and this should be reported on the appropriate case report form.

Health Utilities Questionnaire – ENGLISH

CCTG Trial: **CO.28**

This **page** to be completed by the Clinical Research Associate

Patient Information

CCTG Patient Serial No: _____

Patient Initials: _____
(first-middle-last)

Institution: _____ Investigator: _____

Scheduled time to obtain quality of life assessment: please check (✓)

- Within 30 days prior to enrollment
- After 3 cycles of FOLFOX or after 2 cycles of CAPOX
- PRE-Excision 2-4 weeks (FOLFOX) or 3-5 weeks (CAPOX) after last cycle of chemotherapy

After protocol excision. For patients who fail and go onto TME, these times are from TME date:

- 30 days
- 6 months
- 12 months
- 24 months
- 36 months

Were ALL questions answered? Yes No If no, reason: _____

Was assistance required? Yes No If yes, reason: _____

Where was questionnaire completed: home clinic another centre

Comments: _____

Date Completed: _____ - _____ - _____
yyyy mmm dd

*PLEASE ENSURE THIS PAGE IS FOLDED BACK BEFORE HANDING
TO THE PATIENT FOR QUESTIONNAIRE COMPLETION.*

CCTG use only

Logged: _____

Study Coord: _____

Res Assoc: _____

Data Ent'd: _____

Verif: _____

_____ - _____ - _____

_____ - _____ - _____

_____ - _____ - _____

_____ - _____

_____ - _____

This box to be completed by the clinical research associate: Pt. Serial #: _____ Pt. Initials: _____

EQ-5D Questionnaire

CCTG: CO.28

Under each heading, please tick the ONE box that best describes your health TODAY.

MOBILITY

I have no problems in walking about

I have slight problems in walking about

I have moderate problems in walking about

I have severe problems in walking about

I am unable to walk about

SELF-CARE

I have no problems washing or dressing myself

I have slight problems washing or dressing myself

I have moderate problems washing or dressing myself

I have severe problems washing or dressing myself

I am unable to wash or dress myself

USUAL ACTIVITIES (e.g. work, study, housework, family or leisure activities)

I have no problems doing my usual activities

I have slight problems doing my usual activities

I have moderate problems doing my usual activities

I have severe problems doing my usual activities

I am unable to do my usual activities

PAIN / DISCOMFORT

I have no pain or discomfort

I have slight pain or discomfort

I have moderate pain or discomfort

I have severe pain or discomfort

I have extreme pain or discomfort

ANXIETY / DEPRESSION

I am not anxious or depressed

I am slightly anxious or depressed

[figure not shown]
I am moderately anxious or depressed

I am severely anxious or depressed

I am extremely anxious or depressed

- We would like to know how good or bad your health is TODAY.
- This scale is numbered from 0 to 100.
- 100 means the best health you can imagine.
0 means the worst health you can imagine.
- Mark an X on the scale to indicate how your health is TODAY.
- Now, please write the number you marked on the scale in the box below.

YOUR HEALTH TODAY =

Please check to make sure you have answered all questions.

Please fill in your initials to indicate that you have completed this questionnaire: _____
Today's date (Year, Month, Day): _____

Thank you.
Page 2 of 2

Figure 2: Kaplan-Meier Curve for Locoregional Relapse Free Survival	42
Figure 3: Kaplan-Meier Curve for Distant Relapse Free Survival.....	42
Figure 4: Kaplan-Meier Curve for Disease Free Survival.....	42

1. Introduction

This analysis plan describes the final analysis performed by the Canadian Cancer Trials Group (CCTG) for the CO.28 trial. It will be used for the writing of the Canadian Cancer Trials Group study report.

2. Study Description

2.1 Background

Current standard therapy for patients with T1-3 rectal tumours includes radical surgery with Total Mesorectal Excision (TME), and preoperative chemoradiation for patients with T3 tumours or N1 tumours. Although the locoregional relapse rates with modern adjuvant therapy are low (generally 5%), in patients treated with radical resection, ongoing issues with bowel function, incontinence, sexual function and depression persist. These are significantly worse in patients treated with neoadjuvant or adjuvant radiotherapy.

Multiple single arm and randomized phase II studies have explored the use of pelvic chemoradiation followed by Transanal Endoscopic Microsurgery (TEMS) or Transanal Minimally Invasive Surgery (TAMIS) as a means to increase rectal organ preservation for patients with early rectal cancer but neoadjuvant radiation significantly increases wound-healing complications and adversely affects sphincter and sexual function.

Population based studies have documented an increasing use of local excision/minimally invasive surgery in the treatment of T1N0 or T2N0 rectal tumours but a significant proportion of clinical T1-2N0 tumours are pathologically node positive and the literature demonstrates an increased rate of local relapse with local excision versus surgical resection. Neoadjuvant chemotherapy is a potential approach to reduce local and distant relapse for rectal tumours treated with excision alone since it has been shown to reduce locoregional recurrence in stage II/III rectal cancer but without the toxicities of pelvic radiation. There is, however, virtually no prospective experience of neoadjuvant chemotherapy and excision/surgery for early rectal tumours. This phase II trial was designed to determine the outcomes of the patients with stage 1-2 rectal tumours treated with chemotherapy (FOLFOX or CAPOX) followed by minimally invasive surgery (TEMS or TAMIS). The primary endpoint of the study is the rate of organ preservation.

2.2 Study Design

CO.28 is a single arm, two-stage phase II clinical study of FOLFOX/CAPOX as a neoadjuvant treatment for patients with stage I-II (cT1-3ab/N0) rectal cancer. The study is being conducted by the Canadian Cancer Trials Group.

A total of 50 evaluable patients would be enrolled, in a two-stage minimax design with 22 patients accrued in the first stage. The trial would be stopped at the end of the first stage if the number of patients who avoided radical surgery is 10 or less. Otherwise the trial would proceed to the second stage to accrue 28 additional patients. Allowing for a 15% inevaluable rate, the total sample size would be 58 patients.

This study opened to accrue patients on August 22, 2017. On April 19, 2019, 11 of the 19 patients enrolled in the first stage were found to have avoided radical surgery. It was decided the study would proceed to continue accrual of patients to full sample size. The trial was closed to further accrual on May 19, 2020 after 58 patients were accrued.

A final analysis will be performed on a database which will be locked after all patients completed their treatments and all data observed from the patients are cleaned. This plan describes the details of this final analysis.

The CCTG Data and Safety Monitoring Committee (DSMC) has been reviewing safety data annually and as otherwise required. These analyses have been prepared by a CCTG/Queen's Senior Biostatistician.

3. Objectives

3.1 Primary

The primary objective of this study is to determine the organ preservation rate in patients with early (ct1-3a,bN0) rectal cancer treated with neoadjuvant FOLFOX or CAPOX and TEMS or TAMIS.

3.2 Secondary

Secondary objectives are:

- To describe the 3-year Locoregional Relapse Rate (LRR) in patients treated with organ preservation.
- To describe the 3-year Distant Relapse Rate (DRR) in patients treated with organ preservation.
- To describe the 3-year Disease Free Survival (DFS) rate in patients treated with organ preservation.
- To evaluate the rate of post-operative complications following neoadjuvant FOLFOX/CAPOX and tumour excision/surgery.
- To evaluate nature, severity and frequency of acute and long term toxicities in all patients.
- To evaluate Quality of Life (QoL) in all patients.
- To evaluate the cost-effectiveness of the neo-adjuvant chemotherapy approach vs. the current standard approach.

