8.0 CRITERIA FOR MEASUREMENT OF STUDY ENDPOINTS

8.1 Definitions

8.1.1 *Evaluable for Organ Preservation Rate*

All patients treated with FOLFOX or CAPOX and TEMS or TAMIS will be included in the organ preservation rate analysis as primary endpoint of this study.

Organ preservation rate will additionally be calculated for all patients that have received protocol chemotherapy.

8.1.2 *Evaluable for Rectal Cancer Control*

All patients treated with FOLFOX or CAPOX and TEMS or TAMIS will be evaluated for locoregional and distant relapse rate.

Rectal cancer control will additionally be calculated for all patients that have received protocol chemotherapy.

8.1.3 *Evaluable for Disease Free Survival*

All patients treated with FOLFOX or CAPOX and TEMS or TAMIS will be evaluable for assessment of disease free survival.

Disease Free Survival will additionally be calculated for all patients that have received protocol chemotherapy.

8.1.4 *Evaluable for Post-Operative Complications*

All patients treated with FOLFOX or CAPOX and tumour excision/surgery will be evaluable for post-operative complications.

8.1.5 *Evaluable For Adverse Events*

All patients who have received at least one dose of protocol chemotherapy will be included in the safety analysis.

8.1.6 *Evaluable for Quality of Life Assessment*

All patients who have completed a quality of life questionnaire are evaluable for quality of life.

8.2 *Evidence of Disease Progression/No Response After Chemotherapy*

8.2.1 *Progression*

The diagnosis of progressive disease will be made by treating surgeon after review of the pre-excision (post-chemotherapy) MRI and endoscopy.

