8.3 Organ Preservation Rate

Organ preservation rate is defined as the proportion of patients who avoid TME.

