4.3 Safety

The safety endpoints are post-operative complication rate, serious and non-serious adverse events (clinical and laboratory), laboratory parameters, dosing data (including dose interruptions, total delivered dose and dose modifications) and reasons off treatment.

5. Sample Size and Power

The expected organ preservation rate is 50-68% among patients with clinical T1-3N0 rectal tumours treated with chemoradiation and minimally invasive surgery. Based on these historic phase II data, the experimental treatment would be considered of no interest if the protocol specified organ preservation rate is 50% or lower (H_0) and as promising if its avoidance rate is 65% or higher (H_1).

An optimal two-stage minimax design would be used to test the above hypotheses, which would accrual 22 evaluable patients in the first stage. The trial would be stopped at the end of the first stage if the number of patients who avoided radical surgery is 10 or less. Otherwise the trial would proceed to the second stage to accrue 28 additional evaluable patients. The experimental procedure would be considered as promising if, out of the total patients accrued, 30 or more patients avoided radical surgery. The exact type I error rate and power of this design are respectively 0.1 and 0.8. Allowing for a 15% inevaluable rate, the total sample size would be 58 patients.

6. Data Set Descriptions

Five types of analysis samples will be used:

1. All Accrued Patients:

All patients accrued in the study.

2. All Chemotherapy Treated Patients:

All patients who have received at least one dose of FOLFOX or CAPOX.

3. All Chemotherapy & Excision Treated Patients

All patients who have received at least one dose of FOLFOX or CAPOX and TEMS or TAMIS.

4. All Chemotherapy & Excision/Surgery Treated Patients

All patients who have received at least one dose of FOLFOX or CAPOX and excision (TEMS or TAMIS) or surgery (TME).

5. All Quality of Life Evaluable Patients

All patients who have completed at least one quality of life questionnaire.

7. Statistical Analysis

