7.7 Efficacy

7.7.1 Organ Preservation Rate

After completion of neoadjuvant chemotherapy, the protocol requires that patients with lesions that on pre-excision (post-chemotherapy) MRI and/or endoscopy showing evidence of progression or no response to chemotherapy to be treated with immediately

the radical TME surgery. Other patients will be treated with local excision TEMS or TAMIS. Patients with ypstage T0/T1goodN0 tumours based on local pathology ypstaging review after TEMS or TAMIS are treated with surveillance while patients with tumours with ypT2, N+ or ypT1 tumours with poor prognostic features are treated with radical TME surgery within 6-8 weeks after local excision. The numbers of enrolled patients who were treated with respectively neoadjuvant chemotherapy, TME and TEMS or TAMIS immediately after completion of neoadjuvant chemotherapy, and TME or surveillance after TEMS or TAMIS will be summarized (**Table 30**).

Organ preservation rate, the primary endpoint of this study, is defined as the proportion of patients with tumour downstaging to ypT0/T1good N0 who avoid radical surgery (TME) among all patients treated with FOLFOX or CAPOX and TEMS or TAMIS. The 95% confidence interval for the organ preservation rate will be calculated (**Table 30**).

Organ preservation rate will additionally be calculated among all patients that have received neoadjuvant chemotherapy.

7.7.2 3 Year Loco-Regional Relapse Rate

Locoregional relapse is defined as reappearance of a tumour within the rectum or pelvis. The number of patients with each site (rectum, pelvis, pelvic lymph nodes, and others) of locoregional relapse will be summarized (**Table 31**).

Locoregional relapse free survival is calculated as time from complete tumour surgical excision date (with pathology results negative for malignant disease within 1 mm of surgical margins) to the first date of definitive evidence (clinical, radiological or pathological) of locoregional relapses. Patients with distant relapse only, died, loss to follow up, or alive at clinical cut-off will be censored at respectively last date of distant relapses, date of death, date of lost to follow-up, and last disease assessment date calculated as the last of dates of attendance/last contact on Follow-up Report.

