Kaplan-Meier method (**Figure 2**) will be used to estimate the 3 year loco-regional relapse rate and associated 95% confidence interval first among all patients treated with FOLFOX or CAPOX and TEMS or TAMIS (**Table 31**) and additionally among all patients that have received neoadjuvant chemotherapy.

7.7.3 3 Year Distant Relapse Rate

Distant relapse is defined as appearance of rectal cancer disease at sites remote from the rectum. The number of patients with each site of distant relapse (Lung, Liver, Brain, Distant lymph nodes, Bone, Skin, Ascites, Pleural effusion, Adrenal glands, Other) will be summarized (**Table 31**).

Distant relapse free survival is calculated as time from complete tumour surgical excision date (with pathology results negative for malignant disease within 1 mm of surgical margins) to the first date of definitive evidence (clinical, radiological or pathological) of distant relapses. Patients died, loss to follow up, or alive at clinical cut-off will be censored at respectively date of death, date of lost to follow-up, and last disease assessment date calculated as the last of dates of attendance/last contact on CRD Follow-up Report.

Kaplan-Meier method (**Figure 3**) will be used to estimate the 3 year distant relapse rate and associated 95% confidence interval first among all patients treated with FOLFOX

or CAPOX and TEMS or TAMIS (**Table 31**) and additionally among all patients that have received neoadjuvant chemotherapy.

7.7.4 3 year Disease Free Survival

Disease-Free Survival (DFS) is defined as the interval from complete tumour surgical excision date (with pathology results negative for malignant disease within 1 mm of surgical margins) to date of first occurrence of the events in the below.

- Locoregional relapse reported in CRF Relapse Report
- Distant disease reported in CRF Relapse Report
- Non-protocol radiotherapy, chemotherapy, or biologic therapy without documentation of the site of failure and reported in CRF Chemotherapy Report, Pre-Excision Report, and Surgery Report
- Death due to any other reason reported in CRF Death Report

Patients who are alive without locoregional or distant relapse or receiving non-protocol radiotherapy, chemotherapy, or biologic therapy without documentation of the site of failure at the analysis data cutoff date will be censored at their last disease assessment date calculated as the last of dates of attendance/last contact on Follow-up Report.

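### Secondary objectives 1–3 concern organ-preserved patients, but no planned output reports 3-year relapse or disease-free survival in patients who kept the rectum

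*SAP*

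**What the plan says.** **Objectives.** SAP 3.2 (and Protocol 1.2) lists "To describe the 3-year Locoregional Relapse Rate (LRR) in patients treated with organ preservation". The second objective, for distant relapse, reads "To describe the 3-year Distant Relapse Rate (DRR) in patients treated with organ preservation"; the third, for DFS, reads "To describe the 3-year Disease Free Survival (DFS) rate in patients treated with organ preservation". Protocol 13.1 repeats this population.

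**Definition.** Protocol 8.3: "Organ preservation rate is defined as the proportion of patients who avoid TME". SAP 7.7.1 is narrower: "the proportion of patients with tumour downstaging to ypT0/T1good N0 who avoid radical surgery (TME) among all patients treated with FOLFOX or CAPOX", with the denominator further restricted to those who had local excision. Protocol 13.2 likewise requires both the downstaging and no radical surgery.

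**Analysis sets.** Protocol 8.1.2: "All patients treated with FOLFOX or CAPOX and TEMS or TAMIS will be evaluated for locoregional and distant relapse rate"; 8.1.3 says the same for DFS. SAP section 6 defines the matching data set as "All patients who have received at least one dose of FOLFOX or CAPOX and TEMS or TAMIS", with no exclusion for later TME. SAP 7.7.2 to 7.7.4 estimate LRR, DRR and DFS "first among all patients treated with FOLFOX or CAPOX and TEMS or TAMIS", and additionally in all chemotherapy-treated patients. Table 31 uses the first set, and the note under Figure 4 repeats the table and figures for the second.

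**Pathway.** Protocol 7.3 and SAP 7.7.1 send patients with ypT2, node-positive or poor-feature ypT1 tumours from TEMS/TAMIS to TME (Protocol 7.3 also lists ypT3). Those with ypT0 or good-feature ypT1, N0, go to surveillance. Table 30 has a row for subsequent TME.

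**The concern.** TME after TEMS/TAMIS is a planned branch of the pathway, so the set used for the three secondary endpoints mixes two groups: patients left with a rectum under surveillance, and patients whose rectum was removed. The objectives name the first group. The only other planned set is wider, since it also takes in patients who went straight to TME.

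The background section of the protocol treats ypT0/T1 as a surrogate of locoregional control and notes that local excision cannot clear the nodes completely. Relapse among the ypT0/T1good N0 patients under surveillance is therefore the direct test of the strategy. It is also the figure that the randomized trial foreseen in the protocol would need.

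Pooling has two further effects:

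- Scheduled detection differs. Under the notes to the Protocol 5.0 flowsheet, patients who had TME do not need the pelvic MRIs at months 6, 18 and 30, and need endoscopy only at month 36.
- For a patient who has TEMS/TAMIS and then TME, neither document says which operation is the complete excision date that starts the clock.

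**Working it through.** **1. The plan's own figures.** No precision or sample-size figure is given for the 3-year endpoints. The primary design (Protocol 13.3) is 22 patients, then 28 more, stopping if 10 or fewer avoid radical surgery, with success at 30 or more of 50. The exact probability of success is

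P(success) = Σ P(X1 = x) · P(X2 ≥ 30 − x), for x = 11 to 22, with X1 ~ Bin(22, p) and X2 ~ Bin(28, p).

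- p = 0.50: 0.0977 (stated 0.1)
- p = 0.65: 0.8022 (stated 0.8)
- early stop, P(X1 ≤ 10) at p = 0.50: 0.4159 (stated 42%)

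The design reproduces, so its rates and its 50 evaluable patients are used below.

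**2. Objective against analysis set.**

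- Objective: treated with organ preservation.
- Organ preservation: no TME (Protocol 8.3), or ypT0/T1good N0 and no TME (SAP 7.7.1).
- First analysis set: chemotherapy and TEMS/TAMIS, whatever followed.
- Additional set: any chemotherapy.

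On the SAP definition the objective population is a strict subset of the first set once any patient goes on to TME. Neither set, and no table shell or figure, isolates it.

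**3. Size of the mixing.** SAP 7.7.1 gives the primary rate the same TEMS/TAMIS denominator, so the share of that set without organ preservation is 1 − p. With 50 such patients:

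- H0, p = 0.50: 25 preserved, 25 not (50%)
- success boundary, 30/50 = 0.60: 30 preserved, 20 not (40%)
- H1, p = 0.65: 32–33 preserved, 17–18 not (35%)

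If some patients decline recommended TME, the share who actually had TME is lower by that number.

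**4. Direction.** Ignoring censoring, let a be the 3-year LRR in preserved patients and b the rate in those who went on to TME. Then

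pooled = p·a + (1 − p)·b, and pooled − a = (1 − p)(b − a).

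The sign depends only on whether b is above or below a, and the documents give neither for this population. The values below are assumptions:

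- a = 8%, b = 5%: 0.65×8 + 0.35×5 = 6.95% at H1; 0.50×8 + 0.50×5 = 6.5% at H0. The pooled rate is too low.
- a = 18%, b = 5%: 0.65×18 + 0.35×5 = 13.45%; 0.50×18 + 0.50×5 = 11.5%. The pooled rate is too low.
- a = 8%, b = 10%: 0.65×8 + 0.35×10 = 8.7%; 0.50×8 + 0.50×10 = 9.0%. The pooled rate is too high.
- a = b: no difference.

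**5. Precision of the added row.** Suppose four relapses, all in preserved patients (Clopper-Pearson 95% intervals, ignoring censoring):

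- 4/50 = 8.0% (2.2 to 19.2)
- 4/33 = 12.1% (3.4 to 28.2)
- 4/25 = 16.0% (4.5 to 36.1)

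**The case against.** **The set is pre-specified and consistent.** Protocol 8.1.2 and 8.1.3 name it, the SAP follows it without deviation, and it is the primary endpoint's denominator. The objectives could be read as meaning that preservation was attempted: the background uses organ preservation as the name of a strategy, and the definitions cited above are of the rate. This reading is possible. But neither document states it, and it sits badly with Protocol 8.3 and SAP 7.7.1. If it is intended, the objectives need to say so.

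**Bias in a favourable direction.** A reader might infer that pooling in TME patients flatters the result. Taking the background rates of 5%, 8% and 18%, the reader could put the understatement at about 1 point (8 − 6.95) to 6.5 points (18 − 11.5). The documents do not support that:

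- The 8% comes from T1 tumours treated by local excision alone. The 18% comes from T2 tumours treated by excision plus chemoradiation. The 5% is a general rate with modern adjuvant therapy. None describes ypT0/T1good N0 after chemotherapy, or TME after an adverse specimen, and none is stated as a 3-year rate.
- The background reports rising nodal and locoregional risk from ypT2 upward after chemoradiation. It also cites a randomized trial with similar local and distant control after modified TEMS and TME. Pooling could therefore raise the reported rate, or leave it unchanged.

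**A responder subset should not replace the protocol-defined set.** This stands. The subset conditions on post-treatment pathology and is small. Defining it loosely as patients without TME would also remove those who relapse and then have salvage TME, which deletes the events of interest. The existing set keeps its place as the description of everyone who entered the excision pathway.

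**Conclusion.** The mismatch is real. Three stated secondary objectives name a population that no planned output reports, and by the design's own rates about 35% (H1) to 50% (H0) of the set used instead is outside it. That range assumes that the design rates apply to the TEMS/TAMIS denominator, as SAP 7.7.1 has it, and that nearly all patients with an adverse specimen go on to TME.

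It does not follow that the planned LRR, DRR or DFS will look too good, or by how much. Patients who go on to TME have worse pathology and more surgery, and the documents contain no rates for either group. Nor does it follow that the planned analyses are wrong to keep. The primary endpoint and the sample size are unaffected.

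**What to change.** - Add to Table 31 and Figures 2–4 Kaplan-Meier LRR, DRR and DFS for patients with ypT0/T1good N0 after TEMS/TAMIS who were assigned to surveillance.
- Fix membership by the initial post-excision local pathology and decision, so that later salvage TME for relapse does not remove a patient.
- Show separately the patients who declined recommended TME (a category already in Table 27). They kept the rectum but do not meet the ypT0/T1good N0 criterion.
- Keep the TEMS/TAMIS and chemotherapy-treated sets as they are, and state in SAP 7.7 which row answers objectives 1–3. If the sponsor means attempted preservation, say so in the objectives.
- Settle this before the outcome data are examined.

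The cost is one more data set, an added block in Table 31 and one more curve per figure, all from data already collected. The downside is precision: about 25–33 patients if 50 have TEMS/TAMIS, so the intervals should be presented as descriptive.
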